#### **8.2.2 Blood Tests**

In part A, blood tests (FBC, LFTs, U&Es, CRP) are submitted as outlined in table 2. In part B, blood tests are submitted as outlined in table 3.

## 9 ADVERSE EVENTS

The Investigator is responsible for the detection and documentation of events meeting the criteria and definitions detailed below.

Full details of contraindications and side effects that have been reported following administration of the IMP can be found in the Investigator's Brochure (IB).

Participants will be instructed to contact their Investigator at any time after consenting to join the trial if any symptoms develop. All adverse events (AE) that occur after joining the trial must be reported in detail in the Case Report Form (CRF) or AE form. In the case of an AE, the Investigator should initiate the appropriate treatment according to their medical judgment. Participants with AEs present at the last visit must be followed up until resolution of the event.

### 9.1 DEFINITIONS

An **adverse event** (AE) is any untoward medical occurrence in a clinical trial participant which does not necessarily have a causal relationship with an investigational medicinal product (IMP).

An **adverse reaction** (AR) is any untoward and unintended response to an IMP which is related to any dose administered to that participant.

A **serious adverse event** (SAE), **serious adverse reaction** (SAR). Any AE or AR that at any dose:

- results in death of the clinical trial participant;
- is life threatening\*;
- requires in-patient hospitalisation^ or prolongation of existing hospitalisation;
- results in persistent or significant disability or incapacity;
- consists of a congenital anomaly or birth defect;
- results in any other significant medical event not meeting the criteria above.

\*Life-threatening in the definition of an SAE or SAR refers to an event where the participant was at risk of death at the time of the event. It does not refer to an event which hypothetically might have caused death if it were more severe.

^Any hospitalisation that was planned prior to inclusion into the study will not meet SAE criteria. Any hospitalisation that is planned post inclusion into the study will meet the SAE criteria.

A **suspected unexpected serious adverse reaction** (SUSAR) is any AR that is classified as serious and is suspected to be caused by the IMP, that it is not consistent with the information about the IMP in the Summary of Product Characteristics (SmPC) or Investigators Brochure.

### 9.2 IDENTIFYING AEs AND SAEs

In part A, all AEs and SAEs will be recorded from the time a participant signs the consent form to take part in the study until 3 days after the participant has been dosed.

For part A, a member of the research team will ask about the occurrence of AEs/SAEs during and on a surveillance call 3 days after the participant is dosed. Open-ended and non-leading verbal questioning of the participant will be used to enquire about AE/SAE occurrence. Participants will also be asked if they have been admitted to hospital, had any accidents, used any new medicines or changed concomitant medication regimens. If there is any doubt as to whether a clinical observation is an AE, the event will be recorded. If the healthy volunteer participant is unavailable by phone at this time, a reasonable number of attempts to contact the participant by telephone will be made to follow up on safety outcomes as described in the consent process.

In part B, all AEs and SAEs will be recorded from the time the NAP is delivered and until 3 days after dosing.

AEs and SAEs may also be identified via information from support departments e.g. laboratories. The laboratory may fax the results directly to ACCORD. Details of the fax number will be placed on the laboratory request form as well as the mobile phone number of the Chief Investigator.

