#### **4.2 B) Delivery of NAP to 3 patients in ICU with pulmonary infiltrates**

ICU patients will be screened daily by ICU research nurses. If they fit the inclusion criteria described in Section 5.3, they or their personal/professional legal representative will be approached by a member of the research team to obtain consent. The attending consultant will also be approached and only after also gaining permission from the attending consultant will the patient be considered for inclusion into the study.

The pulmonary infiltrates will be identified on a CXR, which has been performed as part of routine clinical care and bronchoscopy and pCLE performed as above. A CXR will be performed immediately before the procedure. pCLE will be performed on areas without infiltrates as well as the affected segment/s. Following this, NAP will be instilled into the affected segment/s and unaffected segment/s via a microcatheter . A total of 80 mcg ( $\pm$ 20%) of NAP will be delivered

to the patient divided between the affected and unaffected segments. pCLE will be subsequently performed on the segments in which NAP has been delivered. We have performed bronchoscopy in over 70 patients in ICU over the last 5 years. The whole procedure including delivery of NAP will take approximately 30 minutes. The table below summarise the events and data to be collected before and after the procedure.

In addition, we intend to collect an additional sample (less than 5 ml) at  $t = 7.5$  mins ( $\pm 2.5$  mins) for analysis to demonstrate the systemic uptake, or lack thereof, of the IMP. For these participants, the urometer will be emptied at the time of bronchoscopy and then any urine passed over the next 2 hours will be collected to demonstrate the systemic uptake, or lack thereof, of the IMP.

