#### **11.4.1.3 Bronchoscopy and pCLE**

Participants will be closely monitored during and after the bronchoscopy. Healthy volunteers in part A will receive topical anaesthesia to the oral cavity (to prevent discomfort). The subject will also be offered light sedation in the form of intravenous midazolam.

Bronchoscopy can be associated with low oxygen levels (rarely). Prior to bronchoscopy subjects will be given supplemental oxygen. The test will be stopped if the oxygen levels fall significantly. Predefined stopping criteria are established and if oxygen levels as measured by pulse oximetry falls to <92% from baseline, bronchoscopy will be stopped.

Other risks of bronchoscopy include aspiration (in the rare event of vomiting while there are significant gastric contents) and arrhythmia if too much local anaesthetic is used. We have minimised the risk of vomiting firstly by offering 'non-sedated' bronchoscopy (thereby eliminating midazolam, the principal cause of nausea), and secondly by ensuring at least 8 hours between the patient's breakfast and bronchoscopy. The risk of arrhythmia will be minimised by limiting airway anaesthesia to  $\leq 10$ ml 2% lignocaine and by the fact that we study healthy volunteers (in whom arrhythmia is extremely rare).

For part A, bronchoscopy will be undertaken in a dedicated bronchoscopy suite. All the necessary facilities to safely undertake this procedure are available. For part B, bronchoscopy will be performed in ICU.

Subjects can experience cough and fever within 24 hours following bronchoscopy. Subjects will be advised how to manage symptoms (paracetamol as anti-pyretic and analgesia) and given a telephone number to contact a member of the study team if any symptoms develop after leaving hospital.

pCLE has been performed in over 500 patients worldwide with no recorded serious adverse events. It is now a routine procedure in many institutions. We have performed it locally in ventilated animals and patients with no adverse events.

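### Section 9.2 starts Part B adverse-event recording at NAP delivery, while Section 9 requires every adverse event after joining the trial, so non-serious events from the pre-NAP bronchoscopy and first pCLE can go unrecorded.

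*Protocol*

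**What the plan says.** Section 9 sets a general rule for the whole study: "All adverse events (AE) that occur after joining the trial must be reported in detail". The sentence before it ties joining to consent: "Participants will be instructed to contact their Investigator at any time after consenting to join the trial if any symptoms develop". Neither sentence separates Part A from Part B.

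Section 9.2 then gives each part its own recording window. For the volunteers: "In part A, all AEs and SAEs will be recorded from the time a participant signs the consent form". For the ICU patients: "In part B, all AEs and SAEs will be recorded from the time the NAP is delivered and until 3 days after dosing". Both windows end 3 days after dosing. No reason is given for the different starts, and the Part B sentence is not presented as an exception to Section 9.

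Section 9.1 defines an adverse event as "any untoward medical occurrence in a clinical trial participant which does not necessarily have a causal relationship with an investigational medicinal product", so a causal link to NAP is not needed. Section 2.2.2 makes the occurrence of AEs and SAEs the secondary endpoint.

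**The concern.** In Part B the bronchoscope is passed and a first set of pCLE images is taken before any NAP reaches the lung. These are study procedures: the Part B eligibility criteria (5.3 and the Part B exclusion list) do not require a clinically indicated bronchoscopy. Section 11.4.1.3 itself names low oxygen levels, aspiration and arrhythmia as bronchoscopy risks, and any of them could arise before instillation.

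Staff who apply Section 9.2 as written need not log such an event if it is non-serious. Staff who apply Section 9 must log it. The secondary endpoint then depends on which sentence is followed, and under Section 9.2 it is under-counted in ventilated patients. The same event in a healthy volunteer would be counted, so the two parts would be tabulated under different rules.

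**Working it through.** The check sets the recording rules beside the order of procedures. No sample size, power or event count is involved, and the protocol gives no figure of its own to reproduce.

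**1. Recording rules**

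| Section | Applies to | Start | End |
|---|---|---|---|
| 9 | Both parts | Joining the trial, tied to consent | Not given in that sentence |
| 9.2 | Part A | Signed consent | 3 days after dosing |
| 9.2 | Part B | NAP delivery | 3 days after dosing |
| 9.3 | Both parts, AEs and SAEs | When the event occurs; no window set | Not given |
| 9.5 | Both parts, SAEs only | When the investigator learns of the SAE; no dosing condition | Not given |

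**2. Order of events in Part B**

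- Consent comes before any protocol-specific procedure (12.3.1).
- A chest X-ray is taken immediately before the procedure (4.2).
- Bronchoscopy and the first pCLE follow, then NAP: "pCLE will be performed on areas without infiltrates as well as the affected segment/s. Following this, NAP will be instilled into the affected segment/s".
- pCLE is repeated on the segments that received NAP (4.2).

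**3. The interval between the two starts**

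Under Section 9 recording starts at consent; under Section 9.2 it starts at NAP delivery. The interval between them contains the wait from consent to the procedure, the bronchoscope insertion and the first pCLE round. An AE that begins there is mandatory under Section 9 and outside the window in Section 9.2.

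**4. A procedure stopped early**

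Section 11.4.1.3 states: "Predefined stopping criteria are established and if oxygen levels as measured by pulse oximetry falls to <92% from baseline, bronchoscopy will be stopped". That sentence is not limited to Part A. If a Part B procedure stops before instillation, there is no NAP delivery. The Section 9.2 window then has no start, and its end, which is counted from dosing, is undefined.

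**5. Size**

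- Participants under the later start: 3 / (6 + 3) = 3/9 = 33%, which is all of Part B.
- pCLE rounds before the window opens: 1 before NAP out of 1 before + 1 after = 1 of 2 in each patient.
- Procedure time before the window: Section 4.2 gives about 30 minutes for the whole procedure and no split, so the pre-NAP part is more than 0 and less than 30 minutes. The time from consent to procedure comes on top and is not stated.
- Events missed: not estimable, because the protocol gives no event rate for this interval.

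**6. What other sections recover**

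Section 9.5 covers SAEs regardless of dosing. Section 9.3 describes what to do when an AE or SAE occurs but does not settle which window governs. What is left is mainly non-serious AEs before NAP.

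**The case against.** The strongest reply is that the later start is deliberate. Section 9.2 sets the two parts separately and explicitly, and the secondary objective (2.1.2) is whether NAP is non-toxic. An event before NAP cannot be caused by NAP, and a consent start in ventilated patients would collect background ICU events that say little about the product. This is a fair case for a narrower window, but it does not remove the contradiction, because Section 9 still requires the opposite. Nor is the endpoint (2.2.2) or the AE definition (9.1) limited to events caused by NAP. If the specific clause is taken to override the general one, pre-NAP procedural events are excluded, and that is the gap described.

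A second reply is that other provisions catch these events:

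- Section 6.6 requires the reason for a premature discontinuation to be entered in the CRF, so the event behind a stopped bronchoscopy would leave a trace. It need not be recorded as an AE, and the endpoint counts AEs.
- Part B patients are continually monitored (8.2.1), and Table 3 collects blood gases, observations and ventilator settings within 1 hour before the procedure and at 2, 6 and 24 hours after. A lasting effect could therefore show in those data. Observing a change does not make it a recorded AE, and a brief event could resolve before 2 hours.
- Sections 9.5 and 9.3 narrow the gap as set out in the working. That part of the objection stands.

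A third reply is that the protocol plans no comparison of AE counts between the parts, and that healthy men aged 18 to 40 and ventilated patients would differ under any common rule. This also stands in part. The difference between the parts is a matter of consistent tabulation, not a threatened test. The under-count within Part B does not depend on it.

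**Conclusion.** The contradiction is real and lies in the current text: Section 9 and the Part B sentence of Section 9.2 cannot both be followed for an event between consent and NAP delivery. The effect is modest. It concerns 3 of 9 participants (33%), one of two pCLE rounds in each, under 30 minutes of procedure time plus an unstated wait after consent, and mainly non-serious events. No number of lost events can be given.

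The conclusion assumes that joining the trial means consenting, as the preceding sentence in Section 9 indicates. It also assumes that some staff will follow Section 9.2 as the more specific rule. If all staff followed Section 9, nothing would be lost, but Section 9.2 would still be misstated. Because the secondary endpoint is affected and the correction is small, it should be made.

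**What to change.** Reconcile Section 9.2 with Section 9, in one of two ways:

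- **Start at consent.** Record Part B AEs and SAEs from consent by the patient or the legal representative. This agrees with Section 9 and with Part A.
- **Start at the study bronchoscopy.** Record from the start of that procedure at the latest, and add the Part B exception to Section 9. This leaves out most background ICU events before the procedure and still captures procedural ones.

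Under either choice, end the window 3 days after the procedure, whether or not NAP was given, so that a patient whose bronchoscopy is stopped early still has a defined window.

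The cost is one sentence in Section 9.2, plus one in Section 9 under the second choice, and a few more background ICU events to log in three patients.

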### 9.3 RECORDING AEs AND SAEs

When an AE/SAE occurs, it is the responsibility of the Investigator to review all documentation (e.g. hospital notes, laboratory and diagnostic reports) related to the event. The Investigator will then record all relevant information in the CRF and on the SAE form (if the AE meets the criteria of serious).

Information to be collected includes dose, type of event, onset date, Investigator assessment of severity and causality, date of resolution as well as treatment required, investigations needed and outcome.

### 9.4 ASSESSMENT OF AEs AND SAEs

Seriousness, causality, severity and expectedness will be assessed by the Chief Investigator. The Investigator is responsible for assessing each AE.

The Chief Investigator (CI) may not downgrade an event that has been assessed by an Investigator as an SAE or SUSAR, but can upgrade an AE to an SAE, SAR or SUSAR if appropriate.

#### 9.4.1 Assessment of Seriousness

The Investigator will make an assessment of seriousness as defined in Section 9.1.

#### 9.4.2 Assessment of Causality

The Investigator will make an assessment of whether the AE/SAE is likely to be related to the IMP according to the definitions below.

- Unrelated: where an event is not considered to be related to the IMP.
- Possibly Related: The nature of the event, the underlying medical condition, concomitant medication or temporal relationship make it possible that the AE has a causal relationship to the study drug. The assessment of causality will be made against the reference safety information found in the Investigators Brochure.

Where non Investigational Medicinal Products (NIMPs) e.g. rescue/escape drugs are given: if the AE is considered to be related to an interaction between the IMP and the NIMP, or where the AE might be linked to either the IMP or the NIMP but cannot be clearly attributed to either one of these, the event will be considered as an AR. Alternative causes such as natural history of the underlying disease, other risk factors and the temporal relationship of the event to the treatment should be considered and investigated.

#### 9.4.3 Assessment of Expectedness

If an event is judged to be an AR, the evaluation of expectedness will be made based on knowledge of the reaction and the relevant product information documented in the IB.

The event may be classed as either:

**Expected**: the AR is consistent with the toxicity of the IMP listed in the IB.

**Unexpected**: the AR is not consistent with the toxicity in the IB.

#### 9.4.4 Assessment of Severity

The Investigator will make an assessment of severity for each AE/SAE and record this on the CRF or SAE form according to one of the following categories:

**Mild**: an event that is easily tolerated by the participant, causing minimal discomfort and not interfering with every day activities.

**Moderate:** an event that is sufficiently discomforting to interfere with normal everyday activities.

**Severe:** an event that prevents normal everyday activities.

Note: the term 'severe', used to describe the intensity, should not be confused with 'serious' which is a regulatory definition based on participant/event outcome or action criteria. For example, a headache may be severe but not serious, while a minor stroke is serious but may not be severe.

## 9.5 REPORTING OF SAEs/SARs/SUSARs

Once the Investigator becomes aware that an SAE has occurred in a study participant, the information will be reported to the ACCORD Research Governance & QA Office **immediately or within 24 hours**. If the Investigator does not have all information regarding an SAE, they should not wait for this additional information before notifying ACCORD. The SAE report form can be updated when the additional information is received.

The SAE report will provide an assessment of causality and expectedness at the time of the initial report to ACCORD according to Sections 10.4.2, Assessment of Causality and 10.4.3, Assessment of Expectedness.

The SAE form will be transmitted by fax to ACCORD on **[name]** or may be transmitted by hand to the office or submitted via email to [[contact]](mailto:[contact]). Only forms in a pdf format will be accepted by ACCORD via email.

Where missing information has not been sent to ACCORD after an initial report, ACCORD will contact the investigator and request the missing information.

All reports faxed to ACCORD and any follow up information will be retained by the Investigator in the Investigator Site File (ISF).

## 9.6 REGULATORY REPORTING REQUIREMENTS

The ACCORD Research Governance & QA Office is responsible for pharmacovigilance reporting on behalf of the co-sponsors (Edinburgh University and NHS Lothian).

The ACCORD Research Governance & QA Office has a legal responsibility to notify the regulatory competent authority and relevant ethics committee (Research Ethics Committee (REC) that approved the trial). Fatal or life threatening SUSARs will be reported no later than 7 calendar days and all other SUSARs will be reported no later than 15 calendar days after ACCORD is first aware of the reaction.

ACCORD will inform Investigators at participating sites of all SUSARs and any other arising safety information.

An Annual Safety Report/Development Safety Update Report will be submitted, by ACCORD, to the regulatory authorities and RECs listing all SARs and SUSARs.

## 9.7 FOLLOW UP PROCEDURES

After initially recording an AE or recording and reporting an SAE, the Investigator will follow each participant until resolution or death of the participant. Follow up information on an SAE will be reported to the ACCORD office.

AEs still present in participants at the last study visit will be monitored until resolution of the event or until no longer medically indicated.

## 10 PREGNANCY

Pregnancy is not considered an AE or SAE; however, the Investigator will collect pregnancy information for female partners of dosed male participants who become pregnant while participating in the study. The Investigator will record the information on a Pregnancy Notification Form and submit this to the ACCORD office within 14 days of being made aware of the pregnancy.

Female partners of dosed male participants who become pregnant while participating in the study will be followed up until following the outcome of the pregnancy.

## **11 TRIAL MANAGEMENT AND OVERSIGHT ARRANGEMENTS**

### **11.1 TRIAL MANAGEMENT GROUP**

The study will be co-ordinated by a Project Management Group, consisting of [name], [name] and [name].

A Delegation Log will be prepared for each site, detailing the responsibilities of each member of staff working on the trial.

### **11.2 DATA MONITORING AND SAFETY COMMITTEE**

An independent DMSC will be established to oversee the safety of subjects in the study. ***They will be informed of every participant's response to NAP.*** The DMSC will comprise local and external experts who will be contacted at the end of each participant's involvement. A decision to proceed will be required after each dosed participant as detailed in a DMSC charter monitored by ACCORD. At the end of part A, a DMSC report will also be sent to the regional ethics panel for recording successful completion of part A.

### **11.3 INSPECTION OF RECORDS**

Investigators and institutions involved in the study will permit trial related monitoring and audits on behalf of the sponsor, REC review, and regulatory inspection(s). In the event of an audit or monitoring, the Investigator agrees to allow the representatives of the sponsor direct access to all study records and source documentation. In the event of regulatory inspection, the Investigator agrees to allow inspectors direct access to all study records and source documentation.

### **11.4 RISK ASSESSMENT**

A comprehensive review and risk assessment of the study will be performed by the PISRC prior to the approval of the study. A contingency plan will be agreed and this will be audited by the CRF QA Manager once the study is underway. An independent risk assessment will be performed by an ACCORD Clinical Trials Monitor to determine if monitoring is required and if so, at what level. An independent risk assessment will also be carried out by the ACCORD Quality Assurance Group to determine if an audit should be performed before/during/after the study and if so, at what locations and at what frequency.

